## **6.0 Setting**

*6.1 Describe the sites or locations where your research team will conduct the research. Consider each of the items listed below:*

- *Identify where your research team will identify and recruit potential subjects.*
- *Identify where the team will perform the research procedures.*
- *Describe the composition and involvement of any community advisory board(s).*
- *For research conducted in other locations, describe:*
  - *Site-specific regulations or customs affecting the research at those locations.*
  - *Local scientific and ethical review structure at those locations. Examples include work in other cultures or ethnic groups (within or outside of the U.S.) and work with churches. The HRPP will provide additional guidance for international research.*

The research will be conducted at Virginia Tech. Our research team will identify and recruit potential research participants and also perform the research procedures in the Human Integrative Physiology (HIP) Laboratory in the Garvin Innovation Building or the Nutrition and Exercise Metabolism (NEM) Laboratory in the research building located on [name] in the CRC.

## **7.0 Study Intervention(s)/Investigational Agent(s)**

*7.1 Describe the study interventions (including behavioral interventions) and/or investigational agents (e.g., drugs or devices) to be used in this study. Consider each of the items listed below:*

- *Drug/Device Handling: If the research involves drugs or devices, describe your plans to store, handle, and administer the drugs or devices so that they will be used only on subjects, and only by authorized investigators.*
- *Describe whether any of the following will be used: microwaves, X-rays, DEXA scans, general anesthesia, or sedation*
- *If control of the drugs or devices used in this protocol will be accomplished by following an established, approved organizational SOP (e.g., Research Pharmacy SOP for the Control of Investigational Drugs, etc.), please reference the SOP in this section.*

The Research does not involve administration of drugs. The research does involve use of Dual-energy x-ray absorptiometry (DXA/DEXA) scans that will be performed at 4 timepoints during the study

*7.2 List the name of all drugs (including any vitamins, supplements, herbs, or nicotine) to be used in the study. Indicate whether they have FDA approval, and list any limitations for their use:*

N/A

*7.3 List all devices, how they will be used, their purpose in the study, and if they will be used in a manner consistent with their approved uses. If they will be used in ways that are not yet FDA approved, indicate whether they need an IDE or a determination that they are exempt from the IDE Determination. If a determination of significant risk or non-significant risk is needed for any of the devices, include the researcher's recommendation for each of those devices:*

The medical devices/equipment used in this study include the DXA and the CGM sensors.

The DXA will be used to assess total body composition. Both devices are FDA approved and the research will involve employment of these devices for approved uses. Scans will be performed only by members of the research staff who are trained and certified bone densitometry

technologists (CBDT) through the International Society of Clinical Densitometry.

The CGM will be used only for research and not diagnostic purposes for the intended FDA approved intent of monitoring blood glucose concentration over several days. Prescriptions are not required to obtain CGM devices from Abbott Laboratories (FreeStyle Libre) if they are to be used for research purposes. [name] has experience using CGM for research purposes as part of ongoing collaborative research projects.

7.4 *If the drug is investigational (has an IND) or the device has an IDE or a claim of abbreviated IDE (non-significant risk device), include the following information:*

- *Identify the holder of the IND/IDE/abbreviated IDE.*
- *Explain procedures followed to comply with sponsor requirements for FDA regulated research for the following:*

FDA Regulation	Applicable to:		
	IND Studies	IDE studies	Abbreviated IDE studies
21 CFR 11	X	X	
21 CFR 54	X	X	
21 CFR 210	X		
21 CFR 211	X		
21 CFR 312	X		
21 CFR 812		X	X
21 CFR 820		X	

N/A

## 8.0 Procedures Involved

### 8.1 Describe and explain the study design:

Sixteen men and sixteen women between the ages of 18 and 40 will be randomly assigned to the peanut intervention or control group (8 men/8 women/group). A computer program with a random number generator will be used by the study coordinator to assign male participants and female participants to the peanut or control group (i.e., each sex will be separately randomized).

As outlined in the table, eligible participants will undergo a 10-wk diet and training regimen designed to promote healthy weight gain. This will include increasing energy intake by 500 additional kcal/day (above their typical weight maintenance diet and accounting for energy requirements of resistance training) through provision of peanut-based whole foods/snacks or high-carbohydrate containing control snacks along

with a supervised rigorous resistance training regimen designed to promote muscle hypertrophy. After providing informed consent, participants will be randomly assigned to the peanut or control group based on sex. Outcome data will include assessment of body mass, total and regional body composition via DXA and body anthropometrics, skinfolds and somatotyping using the International Standards for Anthropometric Assessment (ISAK) (Stewart, Marfell-Jones et al. 2011) along with measures of resting metabolic rate (RMR), circulating hormones and serum/plasma biomarkers. The latter includes measurement of potentially important hormones/ biomarkers of anabolism, stress, overfeeding, and cardiometabolic health. Compliance to the nutrition and exercise regimen will be evaluated at regular intervals and include collection of 3-day food records (performed at baseline and 3-days prior to each assessment point) and physical activity data collected by digital technology (Garmin Vena SQ smart watch and My PT Hub app).

**Dietary Intervention.** The peanut group will be provided with a variety of whole and laboratory-prepared peanut-containing snacks to meet their daily excess energy. Examples of snacks include peanut butter cookies, trail mix, peanut butter banana smoothies, and peanut butter and fruit jam sandwiches that provide 500 kcal (~15 g of protein). The control group will be provided similar 500 kcal high carbohydrate containing snacks (e.g., blueberry muffins, trail mix with chocolate chips and dried fruit, fruit smoothie, etc). A complete list of these snacks is uploaded as supplemental files and will be shown to participants. These snacks will be prepared in the research kitchen in Wallace Hall ([name]). Participants will be encouraged to consume snacks within an hour of resistance training and/or before bed (Phillips and Van Loon 2011). Participants will also undergo weekly assessments to ensure compliance and adequate progress with excess energy that will be adjusted upward with weight gain to avoid the potential effects of acute energy imbalance due to total body/lean mass gain, and help ensure adequate (~0.5 pound/week) but not excessive (>1.5 pounds/week) weight gain. [name] has previously completed a similar diet-induced weight gain protocol in non-athletes; This protocol overfed 14 male (Gentile, Orr et al. 2007) and 3 female (unpublished data) participants ~1000 calories per day over baseline requirements using commercially-available food/beverages as the source of excess daily energy. Both investigators are research dietitians and have extensive experience with assessment of energy balance and with partial- and fully-controlled feeding trials.

**Resistance Training.** Participants will undergo rigorous resistance training three days/week in the NEM laboratory under close supervision. The following will be performed with weight machines (Nautilus) and free weights: leg press, squat, leg extension, leg flexion, toe raise, lat-pull down, dead lift, shoulder press, bench press, bicep curl, triceps extension and abdominal twist/crunch. The overall goal will be to have participants perform 10 sets of exercises that work the major muscle groups each week in accordance with a recently published position stand of the International Universities Strength and Conditioning Association (IUSCA) (Schoenfeld et al 2021) with slightly different set of exercises performed on each of the three days. Participants will begin with light to moderate resistance for 8-15 repetitions, after which resistance will be gradually increased in the next 5 workouts. After that, three to five sets of each exercise will be completed using modified methodology of Bartels et al (Kreider, Klesges et al. 1996) (previously shown to effectively promote weight gain) in accordance with the latest

guidelines for promoting muscle hypertrophy (Schoenfeld et al 2021). . Resistance will be adjusted upward after 8 repetitions are fully executed using proper technique. Participants engaged in a sport or military training activity will be instructed to maintain their normal training throughout the study.

Table 1. Overview of Data Collection

Overview of Data Collection	Baseline	3 wk	7 wk	11 wk
Body Mass (weight)	x	x	x	x
Body Composition by DXA and spot urine sample; Pregnancy test by urine in female participants	x	x	x	x
Skinfolds & circumferences	x			x
Resting metabolic rate-RMR	x	x		x
Blood via venipuncture and Urine vis 24-hr collection				
CBC and TSH	x			
Testosterone (free &total)	x	x	x	x
Growth Hormone	x	x	x	x
Insulin-like growth factor	x	x	x	x
Leptin	x	x	x	x
Insulin	x	x	x	x
Free T4	x	x	x	x
Cortisol	x			x
Ghrelin	x	x	x	x
Urinary creatinine and urinary iodine	x			x
Health outcomes				
Blood Pressure	x	x	x	x
Serum Lipids	x			x
Serum Vitamin D	x			x
Fasting blood glucose	x			x
Continuous glucose monitoring	x			x
Compliance and Fitness Testing				

Strength Testing	x			x
Aerobic Capacity (VO2max) and walking efficiency	x			x
Food Records and Appetite rating for 3-day	x	x	x	x
Vitamin D Food Frequency and Lifestyle Questionnaire	x			
Exercise tracking for 3-days (smart watch)	x	x	x	x
Daily snack tracking logs and exercise logs	↔	↔	↔	→
Questionnaire-Snack acceptability & exit survey				x

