#### Baseline Screening (approximately 45 minutes)

Informed Consent: Participants will be provided an informed consent form following the phone screening and in advance of coming to the laboratory.

Health History: Subjects will be asked to complete a standard health/medical history questionnaire, which will be used to screen for health issues (e.g., coronary or congenital heart disease) or other reasons (medications which influence study results) that would preclude participation (see uploaded Health History Screening Questionnaire). This questionnaire has been used by [name] for clinical studies for the past 17 years.

Physical Activity: Subjects will be asked to complete a questionnaire regarding habitual physical activity and exercise.

Skinfolds: Skinfolds will be measured at specific anatomical sites that include the triceps, subscapular, biceps, iliac crest, supraspinale, abdominale, front thigh, and medial calf using Harpenden skinfold calipers according to ISAK procedures with the sum of skinfolds used as the outcome variable. Anthropometric breadths and girths will be

obtained using a small sliding caliper and a flexible steel tape measure at the epicondylar humerus, epicondylar femur, midarm (relaxed and flexed), waist, hip, and calf. These will be used both as outcome variables and for initial somatotyping at baseline. This will be done by a trained investigator.

**Blood Draw:** If the participant is able to come into the laboratory after a 12-hour overnight fast, blood will be drawn by venipuncture for the following: a CBC, TSH, testosterone (free and total), growth hormone, insulin-like growth factor, leptin, insulin, thyroid hormone, cortisol, ghrelin, blood glucose, and serum cholesterol. Blood will be collected during the baseline session if the participant is not fasted as outlined below. In total, blood will be drawn four times during the study by venipuncture from a vein in the arm. These include baseline, and at 3, 7 and 11 weeks as explained below. Blood will be drawn with the participant seated quietly in a phlebotomy chair. Approximately 20-25 ml will be obtained for screening/baseline.

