**Baseline Laboratory Testing Session (approximately 2 hours and 30 minutes).**

All measurements will be performed in the morning after a 12-hour fast (no caffeine) with the participants instructed not to engage in heavy exercise for 36 hours prior to testing and to adequately hydrate the evening prior. This visit may be split into two shorter visits.

**Resting Metabolic Rate (RMR; also called Resting Energy Expenditure):** Participants will lay supine on a bed. A clear ventilated hood will be placed over their head, neck and shoulders and plastic drapes will be tucked under them to avoid leakage of air. Air will be pulled thru the hood with a pump and their expired air will be measured for oxygen and carbon dioxide content. The number of calories expended will be calculated using the total volume of air expired and the oxygen and carbon dioxide content. The ratio of carbon dioxide produced to oxygen consumed will be used to estimate carbohydrate and fat utilization.

**Blood Pressure:** Blood Pressure will be measured in the right arm using an automatic blood pressure monitor.

**Blood draws and hormone and metabolite analyses:** If blood was not drawn at the screening visit, it will be drawn immediately after the RMR for a CBC and analysis of TSH, testosterone (free and total), growth hormone, insulin-like growth factor, leptin, insulin, thyroid hormone, cortisol, ghrelin, blood glucose and other factors. Blood will be drawn by venipuncture as explained above for screening. Approximately 20-25 ml will be obtained during the screening/baseline visit.

**Body Weight Height and Composition:** Body weight and height will be measured on a digital physician's scale. Percent body fat and fat-free mass will be measured in all subjects via DXA scan.

**Urine sample and pregnancy test:** All participants will be required to provide a small cup of urine immediately before the DXA. The urine will be evaluated for hydration status

via specific density using a refractometer. A pregnancy test will be performed on the urine sample for female participants.

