Study Codes using a combination of letters and numbers will be used to de-identify subjects from their personal information. No obvious identifiers will be stored with the data; the data spreadsheet, however will include each participants age, sex and starting weight as part of the de-identified data. Original de-identified data collection sheets will be stored in a locked file cabinet as part of study records; scans of some de-identified information may be kept in a password-protected electronic file that is accessible only to research personnel. During the active phase of the study, a master document (key) that will contain the participants name, assigned study code and randomization order will be kept in a password-secured file that will be accessible only to the PI, co-investigator, study coordinator (EM) and doctoral student in charge of the study ([name]). The key will be destroyed 6 to 12 months after collection of data from the last participant. De-identified data may be kept indefinitely. Blood and urine samples will be destroyed after 5 years.

*9.5 Please select the identifiers you will obtain (whether directly from participants or from another source), including but not limited to:*

	Name
	Geographical subdivisions smaller than a state, including street address, city, county, precinct, zip code, and equivalent geocodes (note, the initial three digits of a zip code are not considered identifiable)
	Elements of dates (except year) for dates directly related to an individual, including birth date, admission date, discharge date, date of death, and single year of age over 89 and all elements of dates (including year) indicative of such age (note, such ages and elements may be aggregated into a single category of age 90+)
	Phone numbers
	Fax numbers
	Electronic mail addresses (e-mail)
	Social Security numbers
	Medical record numbers
	Health plan beneficiary numbers
	Account numbers
	Certificate/license numbers
	Vehicle identifiers and serial numbers, including license plate numbers

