We will do everything that we can to make sure that study records are kept private. Each participant will be assigned a unique participant code as explained in section 9.4. All data recording sheets and spread sheets will use the subjects' study code. They will not contain the participants' name or date of birth. These will be compiled in a patient research file/chart and stored in a locked file cabinet organized by their unique study code. Their name will be listed only on the phone screening log (which is to be blackened out after they are assigned a participant code), informed consent and on a master participant list that includes the randomization key. The master participant list will be kept in a separate electronic file than the data files; both will be password-protected. The study consents will be kept together in a separate file in a separate location in a locked office. Only authorized study personnel will have access to study data. Results of the study may be published and/or presented at professional conferences. The participants' name or other personal information that would identify them will not be used. All blood collected and post-processed serum and plasma samples will be labeled with the participants unique study code (plus the study visit and date and time of sample collection) and stored in a secure freezer in a locked laboratory until analysis as mentioned in section 9.2. Archives may be kept for up to five years following study analysis. Training of study personnel including graduate students on procedures to ensure secure collection and storage of study data will occur before study initiation.

*19.4 For multi-site studies, describe how data or specimens will be handled and secured for each site (e.g., central or disseminated data storage, data coordinating center):*

N/A

*19.5 Describe the plan for data disposition following the conclusion of the study (e.g., long term maintenance of data, data destruction methods).*

- *What information will be included in the long term storage of data or specimens?*
- *How long will the data or specimens be stored?*
- *Where and how data or specimens will be stored?*
- *Who will have access to the data or specimens during long term storage?*

- *Who is responsible for receipt or transmission of the data or specimens?*
- *How will data or specimens be shared or transported?*
- *When and how will personal identifiers be destroyed?*

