At the start of the screening visit, a team member will provide potential participants with a written copy of the study consent form and review the document with the participant. Participants will be encouraged to ask questions and seek clarification during the phone screening. The participant will then be encouraged to ask questions before providing written consent. As much time as necessary will be devoted to address participant concerns. Once the participant is ready to sign, he/she will be

allowed to sign in a private room near the door where they may also exit the lab if they no longer wish to participate. Screening and informed consent will be performed by the study coordinator or the doctoral student in charge of the study ([name]). Participants will be encouraged to ask questions and seek clarification during the phone screening and before signing the consent at the beginning of the laboratory screening visit.

These steps including time to review the consent before the screening visit, time with study staff to review the protocol and address concerns, and time to sign the consent in a private setting and close to a laboratory exit will help minimize the possibility of coercion or undue influence.

To help gauge the participant's understanding, the team member will ask the participant to explain the study, how often they will be asked to consume the peanut or high-carbohydrate snacks, how many times a week they would need to come to the lab to resistance train and how many lab visits are expected.

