## 25.0 Process to Document Consent in Writing

25.1 *Consult “SOP: Written Documentation of Consent (HRP-091)” for recommended procedures, and describe whether and how consent of the subject will be documented in writing:*

Individuals who respond to the advertisements will be contacted by phone where they will be informed of the general plan of the study and all specific procedures included in the study (previously outlined in section 12). Participants will then be given a chance to ask questions regarding study procedures and risks. Those still interested will be screened over the phone to determine eligibility based on desire to gain weight, current exercise history, dietary restrictions, medication use, history of food allergy, and other criteria outlined in section 12.2 (see uploaded Screening form). Eligible individuals will be sent a copy of the consent form via email to review prior to coming to the lab. They will then be given a chance to ask any questions either by email or during their scheduled screening/baseline visit. Those still interested will be asked to sign the consent during their first visit, before any data is collected. This information is detailed in section 24 above. A copy of the informed consent will be sent to all participants.

25.2 *If the research presents no more than minimal risk of harm to subjects and involves no procedures for which written documentation of consent is normally required outside of the research context, you can request that the IRB waive the requirement to obtain written documentation of consent (e.g., consent to participate is indicated by pressing a button for an online questionnaire – after the consent information is presented and before the questionnaire begins):*

Waiver of written consent to perform the phone screening is requested.  
The phone screening form has been uploaded.

25.3 *If you will document consent in writing, attach a consent document with places for signatures. If you will obtain consent, but not document consent in writing, please attach the consent script or text. Review “CHECKLIST: Waiver of Written Documentation of Consent (HRP-411)” to ensure that you have provided sufficient information. You should use “TEMPLATE CONSENT DOCUMENT (HRP-502)” to create the consent document or script:*

See the attached participant consent form

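### No allocation concealment is described and the stated roles do not provide it: the coordinator who runs the assignment may also enrol, and nothing ties assignment to final eligibility and baseline

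*Combined protocol and SAP*

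**What the plan says.** **Who assigns.** Section 8.1: "A computer program with a random number generator will be used by the study coordinator to assign male participants and female participants". Each sex is randomized separately, with a target of 8 men and 8 women per group.

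**Who enrols.** Section 24.1: "Screening and informed consent will be performed by the study coordinator or the doctoral student in charge of the study".

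**Who can see the order.** Section 9.4 describes a master key in which "the participants name, assigned study code and randomization order will be kept in a password-secured file" during the active phase. The PI, co-investigator, study coordinator and doctoral student can open it. Section 19.3 calls the file a "master participant list that includes the randomization key".

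**When assignment happens.** Section 8.1: "After providing informed consent, participants will be randomly assigned to the peanut or control group based on sex". Section 25.1 places consent at the start: "Those still interested will be asked to sign the consent during their first visit, before any data is collected".

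**When eligibility is known.** Section 12.2 excludes people for abnormal TSH or hemoglobin (described there as obtained at screening), abnormal lipids, high blood pressure and pregnancy, among other criteria. For the screening blood draw, section 8.2 says: "Blood will be collected during the baseline session if the participant is not fasted as outlined below". The baseline session text repeats this: "If blood was not drawn at the screening visit, it will be drawn immediately after the RMR". Blood pressure and the urine pregnancy test are described in the baseline session and not among the screening-visit procedures. The 3-day food records and continuous glucose monitoring (CGM) follow that session.

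**Setting.** Entry is rolling (section 11.1), and participants are told whether they are in the peanut or non-peanut group (section 8.2, Dietary Intervention).

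**The concern.** Randomization protects the comparison of arms only if the person deciding whether and when to enrol a candidate cannot know or influence the next arm. Here one role may both run the assignment and enrol, and both enrolling roles can open the file that holds the order. Several entry criteria need judgement, such as orthopedic limitations and the adequacy of the diet history. With rolling entry these judgements are made one candidate at a time.

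If an enroller knows the next arm, a borderline candidate can be deferred or declined because of it, even without intent. If assignment precedes the last eligibility results, a borderline result can be judged with the arm already known. Selection on motivation or likely adherence is not measured, so the analysis cannot correct for it. With 16 per arm, a few steered entries could matter.

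The exposure is mainly in the between-arm hypothesis of section 2.2 (more efficient gain and better acceptance with peanut foods). The other hypothesis, about half a pound per week on the regimen with either snack, depends much less on who went to which arm.

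**Working it through.** **1. Roles under the two possible readings.** The documents do not say whether the order is prepared in advance or drawn one participant at a time.

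- *Prepared list.* The coordinator and the doctoral student can open the file that holds it, so either could read the next arm before deciding on a candidate.
- *Live draw.* There is no next arm to read, and the file may be only a record of past assignments. The remaining openings are a repeated draw, which would have to be deliberate, and a draw made too early. With a 50:50 draw, one repeat raises the chance of a preferred arm from 0.5 to 1 − 0.5² = 0.75. This shows what the procedure would allow. It does not estimate what would happen.

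The password, study codes and separate files in sections 9.4 and 19.3 protect confidentiality. They do not separate the assignment from those who enrol.

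**2. Order of events.**

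| Step | Where described | Relation to the only stated milestone (consent) |
|---|---|---|
| Consent | 24.1, 25.1 | the milestone itself; precedes all visit data |
| TSH, hemoglobin, lipids, if fasted | 8.2 Baseline Screening | after consent, same visit |
| TSH, hemoglobin, lipids, if not fasted | 8.2 Baseline Laboratory Testing Session | after consent, later session |
| Blood pressure, pregnancy test | 8.2 Baseline Laboratory Testing Session | after consent, later session |
| 3-day food records, CGM | 8.2, following laboratory testing | after the baseline session |

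Assignment may fall anywhere after the first row. Even a person who arrives fasted has two exclusions whose described measurements come at the baseline session.

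**3. Baseline exposure.** Section 4.1 lists 9 primary endpoints. Two of them, energy intake and 24-h glucose, take their baseline at home after the laboratory session. Of these two, only energy intake is self-reported.

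**4. Does the planned split imply a restriction?** Assume independent 50:50 draws and 16 people per sex, as in section 8.1.

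- Exact 8/8 in one sex: C(16,8)/2¹⁶ = 12,870/65,536 = 19.6%.
- Exact 8/8 in both sexes: 0.1964² = 3.9%.
- With 20 per sex (about 10/10, section 14.4): C(20,10)/2²⁰ = 184,756/1,048,576 = 17.6%; both sexes 0.1762² = 3.1%.

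An unrestricted generator would rarely produce the stated split, so some restriction must be intended. None is described. The plan gives no figure of its own on concealment or predictability to reproduce.

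**The case against.** A reader might infer that allocation is in fact unconcealed, or that a forward list is open to the enrolling staff. The documents support neither as fact. They are silent on concealment, and the file in section 9.4 may hold only past assignments. If draws are live, foreknowledge disappears and abuse would need a deliberate repeat. This stands, and it limits the claim to what is described.

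On timing, the wording that assignment follows consent gives an order, not an immediate trigger. Section 8.1 says eligible participants undergo the regimen, and section 12.2 places TSH and hemoglobin at screening and the diet and exercise history before enrollment. The investigators may well intend to assign only after eligibility is settled. But those sentences say who receives the regimen and when some data are collected. None sets a release rule, and section 8.2 itself moves the blood draw to the baseline session for people not fasted.

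A reader might also infer that baseline energy intake will be biased by knowledge of the arm. This is not shown. Both arms receive 500 kcal snacks, the composition difference is not discussed with participants, and everyone knows the study is about weight gain. No clear reason appears why baseline records should shift differently between arms. The effect is possible but minor.

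**Conclusion.** The point holds in this form: no concealment is described, the stated roles and file access do not provide it, and the text permits assignment before final eligibility and baseline. The restriction behind the equal split is implied but not stated; the 3.9% figure rests on independent 50:50 draws and exactly 16 people per sex.

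The size of any resulting bias cannot be given. The documents do not allow an estimate of how often an enroller would act on knowledge of the arm, and the 75% repeat-draw figure is not evidence that anyone would. The part about roles and access is well supported by the text. The part about timing is a gap that the wording leaves open, not a stated intention to assign early. It should be fixed because the remedy is cheap and concealment lost during enrolment cannot be restored by analysis.

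**What to change.** - **Section 8.1.** Have someone who takes no part in screening, diet history or consent generate and hold one list for each sex, with a restriction that matches the equal split and spare entries in case the sexes are not recruited 20/20. Do not disclose its details to enrollers. Section 8.1 says both investigators are dietitians, so state that the holder takes no diet histories.
- **Section 9.4.** Keep unassigned entries out of any file that enrolling staff can open. The key should show an assignment only once it has been made.
- **Sections 8.1 and 8.2.** Release each assignment, time-stamped, only after every exclusion in section 12.2 is confirmed (including blood pressure, pregnancy test, TSH, hemoglobin and lipids) and baseline measures are complete, including the 3-day food records and CGM. Name the 24-hour urine as an exception if it may still be collected in the first study week.

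**What the fix leaves.** An equal-split list in an open-label trial is still partly predictable. An enroller who tracks past arms and always guesses the under-filled one is right in an expected [m + (4^m/C(2m,m) − 1)/2]/(2m) of cases. For m = 8 this is 10.05/16 = 62.8%, and for m = 10 it is 12.34/20 = 61.7%. Withholding the restriction details helps only a little, because the equal split is printed in the protocol.

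If one 10/10 list per sex is stopped at 16, the split is 8/8 with probability 2,025/4,845 = 41.8%, 9/7 either way 2,400/4,845 = 49.5%, and 10/6 either way 420/4,845 = 8.7%. So 91% of cases are within 9/7.

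**Cost.** Protocol wording, one file permission, and a short wait for laboratory results and baseline records before snacks start. Laboratory turnaround is not given. The wait must fit within the 12 to 13 weeks of participation and the roughly one-year study period. If nobody on the team is free of screening and consent, a colleague outside it would have to hold the list.
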